#### 3 STUDY DESCRIPTION

# 3.1 Background

Urolithiasis (kidney stones) affects 1 in 11 people in the United States and pain caused by urolithiasis is a common cause for presentation to the ED in the United States, totaling more than 1 million visits per year. Additionally, up to one in ten patients who present to the ED for kidney stones return to the ED for reevaluation and as many as a third of these patients require admission to the hospital.8 While complications of kidney stones may necessitate treatment with antibiotics, procedural interventions and admission to the hospital, the vast majority of both the initial and repeat ED visits are due to uncontrolled pain but are unlikely to result in procedural intervention. Often, uncontrolled pain may be accompanied with nausea which limits the ability of patients to utilize oral medications both in the ED and at home leading to the frequent need for parenteral medications, commonly opioids and non-steroidal anti-inflammatory medications, to break the cycle of severe pain caused by kidney stones. At U-M, our preliminary data (Appendix Table 1) demonstrates that approximately 50% of patients receive 2 or more doses of parenteral medications to treat kidney stone related pain in the ED. Nationally, diagnosis of kidney stones has been associated with long term opioid use and opioid medications are often prescribed after ED visits related to kidney stones. 10,11 Recent efforts to reduce opioid use and prescribing in the ED has led clinicians to seek alternative therapies to treat severe and refractory pain including the use of regional anesthesia. 1,2

# 3.2 Erector spinae plane block for urolithiasis

The ESPB was first described in 2017 and has gained popularity for its utility as a safe and effective pain control modality for a variety of surgical procedures including abdominal, breast, thoracic and lumbar spine surgery. The ESPB provides analgesia by inhibiting neurotransmission at the dorsal and ventral rami of the thoracic spinal nerves, providing anesthesia to multiple dermatomal levels. 17 The ESPB is especially suited for renal colic because epidural spread has also been noted for local anesthetic agents leading to both visceral and somatic analgesia. 18 The technique has been shown effective for treating the pain associated with percutaneous nephrolithotomy as well. 19 The procedure has also been adopted in the Emergency Department for treating pain from rib and spinous process fractures, herpes zoster, and acute pancreatitis. 20-24 Recent case series described use of the ESPB for treatment of renal colic. Aydin et al. performed a pilot randomized trial of 40 patients evaluating ESPB performed by emergency physicians against non-steroidal anti-inflammatory drugs for renal colic and found that patients in the ESPB group had significantly lower opioid consumption and pain scores measured on a visual analog scale. Of note, patients receiving ESPB in this study had no opioid medication use after the procedure. Likewise, Noble et al. reported a case series of 10 patients whose renal colic was treated with ESPB and concluded that within 30 minutes of the procedure, most patients had total or significant reduction in their pain and that the ESPB was effective in those patients with opioid use disorder. Importantly, in both these studies, no significant complications of the procedure were reported.

# 3.3 Ultrasound guided regional anesthesia in the ED

Ultrasound-guided regional anesthesia (UGRA) encompasses a variety of procedures that can be used in the Emergency Department for treatment of pain and to facilitate procedures. UGRA utilizes real time guidance of anesthetic injection near a target nerve or in the desired fascial plane to cause sensory blockade. UGRA offers effective pain control without the side effects and potential long term abuse potential of opioids. The best studied UGRA plane block technique in in emergency medicine is the fascia iliaca block for treatment of hip fracture related pain. Multiple randomized trials have demonstrated the fascia iliaca block is not only safe and effective for treating pain, but also prevents complicating pneumonia in elderly hip fracture patients and improves functional outcomes. The serratus anterior plane block is another widely used UGRA technique for the treatment of rib fractures in the ED with both demonstrated efficacy and an excellent safety profile. Only 30–32 The ESPB is a similar plane block technique, that has the potential to benefit patients with a variety of painful conditions of the trunk.

# 3.4 Summary of Rationale

- Kidney stones are a common reason for emergency department visits
- Pain related to kidney stones can be incredibly painful and refractory pain may lead to increased use of parenteral medications in the ED as well as increased opioid prescribing
- ESPB is a common plane block utilized by EPs to treat pain with an excellent efficacy and safety profile

# 3.5 Study Aims

- Determine the efficacy of the erector spinae plane block performed by emergency physicians for the treatment of pain related to uncomplicated urolithiasis
- Determine the effect of ESPB on ED operations metrics (disposition, length of stay, return to ED)
- Determine the effect of ESPB on use of opioid medications in the ED and during the follow up period

Estimate rate of complications for ESPB when performed by EPs

#### 3.6 Outcomes

#### 3.6.1 Primary Outcome and rationale

The primary outcome will be the proportion of patients receiving a second parenteral pain medication in the ED after a single-shot ESPB is performed by a study investigator. We have reviewed historical data that suggests that the rate of response (percentage of patients that do not require a second parenteral pain medication) in patients with urolithiasis, and who receive a parenteral medication as the first analgesic in the ED (approximately 70% of all kidney stone patients), ranges from 47 to 57% for the years 2020 – 2022. The average response rate is 53.4% during this period which is in line with historical trends prior to the Covid-19 pandemic.

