# 2.10 Sample Size

- This study is a two-stage trial with one planned interim analysis for futility
- Based on the prior 30-month time period (as of May 2022), 572 out of 1071 patients (53.4%) presenting to the ED and meeting the inclusion criteria did not require a 2nd parenteral pain medication during the ED encounter. Thus, we estimate a baseline response rate of 55%.
- Prior work by Nobel et al.¹and Aydin et al.² suggests that no patient will require a second dose of any pain medication after ESPB, but we estimate a conservative response rate of 75% for treatment with ESPB.
- Using Simon's optimal two-stage design with these parameters and  $\alpha$  = 0.05,  $\beta$  = 0.10, we estimate that 18 subjects will be required at the interim analysis and 54 subjects will be required to complete this study.
- Using a Bayesian two-stage design, where interim analysis is planned at one-third total enrollment and a stopping rule if there is only a 10% probability of ESPB demonstrating a 75% response rate, we estimate that 45 total subjects (15 at interim analysis) will be required to achieve a 1.4% chance of stopping early and 95.2% chance of rejecting the null hypothesis.
- This study will aim to achieve a total enrollment of 60 subjects who receive ESPB to account for losses to follow up and withdrawals from the study. Up to 180 (3:1 ratio) historical controls will also be included in the study thus the total enrollment including both treatment and control patients is 240.

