# 4.4 Selection of external control patients

External control patients will be selected from a population of patients meeting the following criteria: 1) adult ED patient with the diagnosis of uncomplicated kidney stones; 2) received at least one dose of parenteral medication while in the ED; 3) presentation to the ED between 7/1/2021 and the study start date. From this population, propensity score matched control patients will be selected at a ratio of 3 controls to 1 ESPB patient. External control population patients are not active patients in this study and analysis of their data will be secondary use of data collected during routine care. To provide valid comparison between control patients and ESPB patients, we will compare pain scores obtained by the treatment team (bedside nurse). For all other primary and secondary outcomes, data collection utilizes EHR query that does not require prospective data collection. Please see the data collection section of this protocol for further details.

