# 4.6 Screening

- Study team members will screen for patients using the ED track board and other patient lists/reports within MiChart (EPIC EHR)
- Study team members will review potential subjects' presenting symptoms, prior medical history, and imaging findings
- Study team members will then notify a physician investigator on call of potential subjects currently in the ED
- Physician investigator will review inclusion and exclusion criteria with other study team members (if they did not perform screening personally) as well as the potential subject

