# 7.2 Primary analysis

Our primary analysis will evaluate the proportion of patients receiving ESPB who require a second parenteral pain medication. This outcome will be compared to external control patients who are selected using propensity score matching at a ratio of 3:1. The propensity score model will include the following variables: age, gender, triage acuity level (ESI score), first ED pain score assessed by nursing, Charlson Comorbidity Index, chronic and initial pain medication type. Data for this outcome will be collected via EHR query as above.

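### Section 3.6.1 counts the primary outcome from the block, but neither the controls nor the 55% null are on that clock, so the contrast and the futility rule are open to bias of unknown size and direction

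*Combined protocol and SAP*

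**What the plan says.** - **Outcome.** Section 3.6.1: "The primary outcome will be the proportion of patients receiving a second parenteral pain medication in the ED after a single-shot ESPB is performed". Section 7.2 gives no start: "Our primary analysis will evaluate the proportion of patients receiving ESPB who require a second parenteral pain medication". Sections 2.4, 2.8 and 7.3 also refer to a second parenteral medication without saying when counting begins.
- **Null rate.** Section 2.10 reports that "572 out of 1071 patients (53.4%) presenting to the ED and meeting the inclusion criteria did not require" a second "parenteral pain medication during the ED encounter", and rounds this to a 55% baseline response. Section 3.6.1 sets the same 53.4% beside its post-block outcome.
- **ESPB patients.** Section 4.2 requires one parenteral dose in the ED, without saying whether that means exactly one or at least one. Section 4.6 limits the approach to patients who are still there: "Study team members will then notify a physician investigator on call of potential subjects currently in the ED".
- **Controls.** Section 4.4 requires that the patient "received at least one dose of parenteral medication while in the ED", with "presentation to the ED between 7/1/2021 and the study start date". That fixes calendar dates but no index time within the visit.
- **Matching.** The propensity variables in section 7.2 are "age, gender, triage acuity level (ESI score), first ED pain score assessed by nursing, Charlson Comorbidity Index, chronic and initial pain medication type".
- **Data.** Section 5.3 records the block time. Section 6.4 takes medications given and nurse pain scores from one EHR query for both groups.

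**The concern.** Time between the first dose and the block is built into the workflow: imaging, screening, written consent, monitoring and drug preparation come first. Two things can happen in that interval. Some patients receive a second dose. Others do well on the first dose and may leave, or may never be approached. Controls pass through the same interval, but no condition is applied to them at its end.

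Three readings of the plan are possible:

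- **Exactly one dose at entry.** Early re-dosers are kept out of the ESPB group but stay among the controls.
- **Post-block count.** Early re-dosers are enrolled, and their earlier second dose is not counted.
- **Whole-visit count.** Every dose in the visit counts in both groups.

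Under the first two, part of an apparent benefit could be time in which an ESPB patient could not fail. Under the third, ESPB is charged with doses that the block could not have prevented. The same uncertainty reaches the futility rule, because its null comes from a whole-visit count in all dosed patients.

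**Working it through.** **1. The plan's own figures.** 572/1071 = 0.534, so 499/1071 = 0.466 had a second dose. A search for Simon's optimal design with p0 = 0.55, p1 = 0.75, α = 0.05 and β = 0.10 gives 10/18 and 35/54, with α 0.0477, power 0.901 and stopping probability 0.609 under p0. Ten or fewer responders of 18 is the same as eight or more second doses. Sections 2.10 and 7.3 are correct for a 55% null.

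**2. Assumed quantities (not in the documents).**
- f: share of second doses that fall before block time.
- g: share of first-dose responders never enrolled. That early responders are less often blocked is an inference; section 4.2 does not require current pain at enrolment.
- h: share of early re-dosers who are dosed again after the block.

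**3. ESPB response for an inert block,** with R = 0.534 and F = 0.466:
- Exactly one dose: R(1−g) / [R(1−g) + F(1−f)]. This equals R when f = g and exceeds R only if f > g.
- Post-block count: [R(1−g) + F·f(1−h)] / [R(1−g) + F]. This exceeds R only if f(1−h) > R·g.
- Whole visit: r = R(1−g) / [R(1−g) + F]. This never exceeds R. With a block preventing a share e of post-block second doses, the response is r + (1−r)(1−f)e. I take e = 0.20/0.466 = 0.429, which is 20 points at f = g = 0.

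**4. Test.** Exact enumeration, 60 v 180, pooled chi-square without continuity correction, with the stop at 10 or fewer responders of 18. Section 7.1 gives alpha 0.05 without sidedness; I take it as two-sided. Controls are held at the unmatched 53.4%, and the groups are treated as independent.

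Inert block, chance of a significant result favouring ESPB (1.9% with no bias):

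| Reading | f | g | ESPB response | Chance |
|---|---|---|---|---|
| Exactly one dose | 20% | 0 | 0.589 | 9.1% |
| Exactly one dose | 20% | 10% | 0.563 | 4.6% |
| Exactly one dose | 20% | 20% | 0.534 | 1.9% |
| Exactly one dose | 20% | 30% | 0.501 | 0.6% |
| Post-block, h = 0 (upper bound) | 20% | 0 | 0.627 | 21% |
| Post-block, h = 0.5 | 20% | 0 | 0.581 | 7% |
| Post-block, h = 0 | 20% | 20% | 0.583 | 8% |
| Post-block, h = 0.5 | 20% | 20% | 0.531 | 1.7% |
| Whole visit | any | 0 | 0.534 | 1.9% |
| Whole visit | any | 20% | 0.478 | 0.2% |

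Effective block (e = 0.429), whole-visit count:
- f = g = 0: response 0.734, power 76%, futility stop 8%.
- f = 20%, g = 0: response 0.534 + 0.466 × 0.8 × 0.429 = 0.694, power 55%.
- f = g = 20%: r = 0.478, response 0.658. The true effect is 17.9 points (0.658 − 0.478) but 12.3 are seen against controls at 0.534. Power is 35% and the futility stop 25%.

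**5. Futility stop for an inert block,** P(X ≤ 10 of 18): 0.609 at 0.55 and 0.660 at 0.534. Under exactly-one-dose entry it is 0.253 at f = 40%, g = 0 (response 0.656) and 0.814 at f = 0, g = 20% (response 0.478).

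**The case against.** The best defence is that a second dose presupposes a first. A first parenteral dose is an entry condition in both groups (4.2, 4.4), and the same EHR query captures doses in both (6.4, 7.2, 7.4). The first dose is then an implied shared origin. Only section 3.6.1 departs from it, perhaps merely describing the expected order of events. This largely stands. A reader might infer that the outcome has no time origin at all; the documents do not support that. But a first-dose origin does not remove the condition that ESPB patients, unlike controls, must remain in the ED until they are blocked. Nor does it say what happens to a second dose given in between.

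A reader might also infer that the 499 re-dosed patients among the 1071 rule out entry at exactly one dose. They do not. Eligibility is judged at enrolment, whereas those doses were counted over a completed visit; a patient can have one dose at entry and a second later.

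Matching on first pain score and initial medication may adjust in part for re-dosing risk, and the illustration does not model this. None of the listed variables records timing, presence in the ED, or dose count at block time. Figure 1, which covers the workflow, is not shown, so the absence of a rule is a statement about the available text only.

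**Conclusion.** The point holds as a conflict in the outcome definition together with an unmatched condition on reaching the block. Section 3.6.1, followed as written, compares groups over different periods at risk.

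It is tempting to read this as a bias in favour of ESPB. The documents do not support that. Under exactly-one-dose entry or post-block counting, the bias favours ESPB only when early re-dosing outweighs the loss of early responders; otherwise it cancels or reverses. Under whole-visit counting, false positives are not inflated, but a real effect is diluted and more often missed or stopped early.

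The size is unknown. The percentages rest on assumed f, g and h and on an unmatched control rate, so they show sensitivity rather than expected error. The 8-of-18 rule is not miscalculated; the open question is whether its 55% null describes patients still in the ED at block time. The definition should be settled before outcome data are analysed, since otherwise the counting rule could be chosen after the results are known.

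**What to change.** **Needed.**
- Use one outcome wording and one starting point in 2.4, 2.8, 3.6.1, 7.2 and 7.3, and state how a second dose given before the block is counted in the analysis.
- In 4.4 and 7.2, put both groups on the same clock. Give each control an index time equal to its matched ESPB patient's interval from first dose to block. Keep only controls still in the ED with the same number of parenteral pain doses at that time. Count the outcome from there in both groups.
- Keep the whole-encounter comparison as a sensitivity analysis.
- In 2.10, recompute the 53.4% rate in the existing 30-month cohort on the same clock over a stated range of intervals, and recheck the 8-of-18 rule against it.

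**Optional.** Risk-set matching is one way among several to do this. The last nurse pain score before the index time could be added to the propensity model where it is available.

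**Cost.** Protocol wording, medication timestamps added to the planned EHR query, and programming; block time is already recorded. The control pool shrinks, but section 2.10 sets 180 controls as a ceiling, so a matching ratio below 3:1 is acceptable.

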#### 3.6.2 Secondary Outcomes

- Difference in visual analog scale pain (1-10) from prior to procedure to first pain assessment after 60 minutes from completion of ESPB assessed by bedside nurse
  - Historic data from the U-M ED suggests that the median maximal pain reduction (last pain score minus first) in the ED is a mean reduction of 3.4 points (SD = 3.0) from a starting value of 7.9.
- ED operational quality metrics:
  - o Rate of admission to hospital
  - Rate of 72-hour return to the ED
  - ED length of stay
- Safety outcomes and complications at day 30

#### 3.6.3 Exploratory Outcomes

- Difference in highest and lowest pain scores while patient is in the ED
- Opioid pain medication usage measured in intravenous morphine equivalents and proportion of patients that receive a prescription for opioid pain medication
- Immediate complications of ESPB
- Survey follow-up administered online with/without telephone assistance at 1, 7 and 30 days from initial ED visit assessing the following outcomes:
  - Duration of pain control after ESPB (day 1 survey only)
  - o Delayed complications of ESPB (optional except for day 30)
  - Patient satisfaction with pain control and procedure
  - Use of opioid and other pain medication after discharge from the index ED visit

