#### 7.4 Other outcomes

Other outcomes unique to study patients (received ESPB as part of this study) including change in pain score, follow up assessment outcomes, complications, and patient satisfaction will be analyzed before-after the ESPB, change over time, or descriptively as appropriate. Secondary outcomes derived from EHR query (ED operations metrics, opioid medication usage and prescriptions) will be analyzed for study patients in comparison to external controls. All comparisons to external control patients will be made using data collected via EHR query rather than prospectively collected data (investigator collected pain scores, patient satisfaction, follow survey results, etc.) which will be reported descriptively and without comparison to controls.

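### The exploratory highest-versus-lowest ED pain score is a range with no direction that can only grow as scores are added; a signed change from the same nurse scores would be interpretable

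*Combined protocol and SAP*

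**What the plan says.** Section 3.6.3 names the outcome in one line: "Difference in highest and lowest pain scores while patient is in the ED". It gives no time order, sign, window, link to the time of the block, or rule on how many scores are needed. The outcome does not appear in the summary list in section 2.9.

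Section 3.6.2 holds a separate secondary pain outcome that is ordered in time and tied to the block. It runs "from prior to procedure to first pain assessment after 60 minutes from completion of ESPB assessed by bedside nurse". Beneath it stands a historical figure: "median maximal pain reduction (last pain score minus first) in the ED is a mean reduction of 3.4 points", with an SD of 3.0 and a starting value of 7.9.

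Two sections bear on whether pain scores are compared with controls. Section 4.4 says "we will compare pain scores obtained by the treatment team (bedside nurse". Section 7.4 lists "Other outcomes unique to study patients (received ESPB as part of this study) including change in pain score", to be analysed within the treated group. Section 7.4 also confines all control comparisons to data from the EHR query, which under section 6.4 includes nurse pain assessments.

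**The concern.** The natural reading of a pain-score difference in an analgesia trial is relief. A range does not measure relief. It is never negative, so a patient whose pain worsened contributes a positive value. It also depends on how often pain was scored: each extra score can set a new maximum or minimum but can never undo one. Two groups with the same pain course but different numbers of scores will therefore differ on average.

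Section 7.1 applies a 0.05 significance level to all analyses, so a comparison of this outcome with controls would probably be tested and reported. A difference that came only from charting frequency or length of stay could then be read as an effect of the block, or could hide one. Setting the range beside the historical 3.4 points would also put two different quantities side by side.

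**Working it through.** **The plan's own figures.** The documents give no expected value, power or size for this outcome, so there is nothing of its own to reproduce. The only nearby figure is that the historical change "is a mean reduction of 3.4 points (SD = 3.0) from a starting value of 7.9"; its source data are not in the documents, so it is used here as an input. The sample size in section 2.10 rests on the primary outcome alone. An exact search for Simon's optimal design (55% v 75%, α 0.05, β 0.10) returns 18 and 54 patients (attained α 0.0477, power 0.9007), as stated, and nothing about the pain range enters it.

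**Step 1, direction.** For scores y1, ..., yk the outcome is R = max(y) − min(y). For 3 then 9, R = 9 − 3 = 6. For 9 then 3, R = 9 − 3 = 6. The signed change y1 − yk gives −6 and +6.

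**Step 2, size against first-to-last.** Since max ≥ y1 and min ≤ yk, R ≥ y1 − yk. By the same argument R ≥ yk − y1. So for every patient R is at least as large as the first-to-last change in either direction, and the two are different quantities.

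**Step 3, number of readings.** For k independent normal readings with no trend, the expected range is 1.13, 1.69, 2.06, 2.33 and 2.53 reading SDs for k = 2 to 6.

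**Step 4, a calibrated check.** From the documents: start 7.9, mean drop 3.4, SD of drop 3.0 (section 3.6.2); 60 treated patients and 180 controls (section 2.10). Assumed, because the documents are silent: reading-to-reading SD e of 1.0, 1.5 or 2.0; between-patient SD of the start 1.5; a linear course with equally spaced readings; scores rounded and limited to 0–10; and the number of readings. Each patient's true drop has SD √(3.0² − 2e²), so that the observed change has SD 3.0 before rounding and limiting. Both groups have the same true course and differ only in number of readings. Each setting used 4,000 trials and a two-sample t-test.

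| Reading SD | Mean first minus last, 3 readings | Mean range, 3 readings | Mean range, 5 readings | 5 minus 3 | False finding for treated group, 4 v 3 readings | Same, 5 v 3 readings |
|---|---|---|---|---|---|---|
| 1.0 | 3.24 | 3.73 | 4.09 | 0.36 | 8% | 19% |
| 1.5 | 3.18 | 3.94 | 4.61 | 0.67 | 21% | 59% |
| 2.0 | 3.10 | 4.19 | 5.17 | 0.98 | 43% | 90% |

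The nominal rate in the last two columns is 2.5%; with 3 v 3 readings it was 2.5% to 2.8%. The mean change falls a little below 3.4 because scores are limited to 0–10. If the controls have the extra readings, the 5-minus-3 difference changes sign.

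On identical data with three readings, the range exceeds the mean first-to-last change by 3.73 − 3.24 = 0.49, 3.94 − 3.18 = 0.76 and 4.19 − 3.10 = 1.09 points. About 9% of simulated patients end worse than they began, yet their mean range with three readings is 1.99, 2.45 and 2.97 points.

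**Step 5, the signed change.** In the same simulations, first minus last differs between groups by about 0.01 points at most. It gives a false finding in favour of the treated group in 2.2% to 3.0% of trials, whatever the number of readings.

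**The case against.** The strongest reply is that this is one exploratory line, and that section 3.6.2 already supplies a directional, block-anchored pain outcome at a higher tier. That stands, and it limits the weight of the point.

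A reader might go further and infer that the outcome favours ESPB by construction, because treated patients wait for consent, the block and a one-hour check and so collect more scores. The documents do not support this as fact. Section 8.1 names delay as a risk, but section 8.4 names a better length of stay as a possible benefit, and length of stay is itself an outcome. The one-hour check in section 5.4 is made by the study team, and section 7.4 keeps investigator-collected scores out of control comparisons. Controls need at least one parenteral dose, and by section 2.10 about 47% of historical patients (1071 − 572 = 499 of 1071) did receive a second, so many controls were also treated further.

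Nor do the documents say that this outcome will be judged against 3.4. That figure sits under the secondary outcome.

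A larger bias could be computed from trendless scores: at a reading SD of 2.0, 2.0 × (2.33 − 1.69) = 1.28 points for five readings against three. Section 3.6.2 describes falling pain, so the calibrated 0.36 to 0.98 is the better guide. Likewise, three trendless readings give 2.0 × 1.69 = 3.38, close to 3.4, only because of the SD chosen; at 1.5 the result is 2.54.

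Finally, first minus last is not specific to the block, because it includes the effect of the first parenteral dose and of any later drug. That is correct, and the fix must say so.

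**Conclusion.** The point holds in a limited form. That the range lacks direction, cannot fall as readings are added, and equals or exceeds the first-to-last change follows from its definition and needs no assumption. Bias between groups is conditional: it requires a comparison with controls, on which sections 4.4 and 7.4 must be reconciled, and unequal numbers of nurse scores. Its direction is open. Its size, about 0.4 to 1.0 points for five readings against three, rests on the assumed reading SDs, linear course and reading counts. That the range is not comparable with 3.4 rests on the description in section 3.6.2 of that figure as last minus first. The outcome is exploratory; the primary analysis, interim rule and sample size are untouched.

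**What to change.** - **Section 3.6.3:** replace the range with first ED nurse score minus last ED nurse score, taken from the EHR, positive meaning improvement. Report the number of nurse scores per group. State that this whole-visit change includes the effect of the first parenteral dose, so the block-anchored secondary outcome in section 3.6.2 remains the measure of change after the block.
- **Sections 4.4 and 7.4:** state whether change in nurse pain score is compared with controls, and make the two sections agree.
- **Section 3.6.2:** check the 3.4 figure against its source data and correct the description, which now labels one number as a median, a maximal reduction and a mean. The documents do not show which label is right.

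The cost is a few lines of wording; the EHR data are the same. The reported figure will be smaller and look less favourable than the range.
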